**Among patients with moderate/severe CD (at inclusion) and who achieved clinical remission with azathioprine:**

- Median time to loss of clinical remission (PCDAI>11) with azathioprine

**Among patients with mild Crohn's disease at study inclusion** (PCDAI>11<30) with fecal calprotectin levels > 100 ug/g and/or Endoscopic activity (Simple endoscopic score for Crohn's disease [SES-CD]  $\geq 3$ )

- Median time to loss of clinical remission (PCDAI >10 ) with azathioprine
- **Physician reported clinical outcome (PCDAI)** at each data collection time points.

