Two recent Cochrane analyses have synthesized the existing data regarding the efficacy of AZA and 6MP in the induction and maintenance of remission in CD. Prefontaine et al. (2010) assessed eight RCTs of AZA/6MP for induction of remission in 425 patients with active CD. Overall response in the pooled treatment group was 54 versus 33% in the placebo arm (odds ratio [OR], 2.43; 95% CI, 1.62-3.64). In addition to clinical response, five studies reported data on corticosteroid reduction while on these agents, with 76 of 117 (65%) thiopurine-treated patients exhibiting reduced steroid use, compared with 39 of 109 (39%) in the placebo group (OR, 3.69; 95% CI, 2.12-6.42). This meta-analysis was updated in 2013, showing that AZA and 6MP offer no advantage over placebo for induction of remission or clinical improvement in active Crohn's disease. However, the combination of AZA and infliximab was superior to infliximab alone for induction of steroid-free remission.

With respect to maintenance of remission, a recent systematic review assessing seven trials with AZA and one with 6MP demonstrated, among 550 adult patients, an OR of 2.32 (95% CI, 1.55-3.49) for AZA and 3.32 (95% CI, 1.40-7.87) for 6MP. A significant number of patients receiving AZA for maintenance of remission had to stop taking the medication due to intolerance, compared with placebo, with an OR of 3.74 (95% CI, 1.48-9.45).

Markowitz et al shown, in 55 children submitted to induction of remission with corticosteroids and randomized to receive 6MP or placebo at week 8, a 9% relapse in the group treated with 6 MP compared with 47% of the controls during a follow up period of 18 months. However subsequent observational studies have not been able to reproduce these low relapse rates, as relapse rates of 40 to 60% were found with azathioprine.

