## 6.3 DISCONTINUATION FROM OBSERVATION PERIOD

In this study, patients will be followed up to a maximum period of 96 weeks. However, observation may be stopped prior to the 96 weeks for different reasons including, but not limited to:

- Patient discontinues the exposure of interest (azathioprine). The introduction of new treatments to CD during the follow up period will not lead to study discontinuation as long as treatment with azathioprine is not discontinued.
- Protocol violation
- Lost to follow up
- Patient withdrawal of consent
- Pregnancy
- Death

In the case observation period is stopped prior to the 96 weeks, the date of study discontinuation, the date of last intake of azathioprine and dose, and the reason for discontinuation should be recorded in the electronic CRF.

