#### Basal characteristics

- Date of birth
- Sex
- Height
- Weight
- BMI
- Smoking status
- Diagnosis of CD and date

- Date of start of symptoms
- Familial history of IBDs
- Disease presentation (abdominal, constitutional, abdominal + constitutional, anal disease, acute abdomen, fever, anemia, extra-intestinal manifestation, abdominal mass, similar presentation to UC, growth failure)
- Clinical course
- PDAI includes (CD activity): Subjective reporting of the degree of abdominal pain; Presence of extraintestinal manifestations, such as fever, arthritis, rash, and uveitis; Physical examination findings; Weight and height; Hematocrit, erythrocyte sedimentation rate, and serum albumin.  
The scale can be assessed at: [http://www.gedii.pt/\\_scores\\_online](http://www.gedii.pt/_scores_online)
- Routine laboratory parameters (hemoglobin, leukocytes, neutrophils, eosinophiles, basophiles, monocytes, lymphocytes, erythrocyte sedimentation rate, CRP, ferritin, iron and transferrin)
- First episode - Paris classification for CD: age at diagnosis, location, behavior, growth.  
The scale can be assessed at: [http://www.gedii.pt/\\_scores\\_online](http://www.gedii.pt/_scores_online)
- Anal lesion (strictures, abscesses, or fistulas)
- Extra-abdominal manifestations
- Colonoscopy - Simple endoscopic score for Crohn's disease (SES-CD)  
The scale can be assessed at: [http://www.gedii.pt/\\_scores\\_online](http://www.gedii.pt/_scores_online)
- Dose of azathioprine, date of start (Day 1)
- Concomitant therapies (from Day 1)
- Stool sampling - assessment of fecal calprotectin levels:
  - The stools will be sent to a central lab (Departamento de Farmacologia Faculdade Medicina do Porto)
  - Calprotectin testing – sample sent to central laboratory

**Information to be collected at each data collection time points of follow up (every 12 weeks up to week 96) – see Chronogram.**

- Weight/ Height/BMI
- Dose of azathioprine, if changed since previous data collection time point.
- Concomitant therapies (including CD therapies), if changed since previous data collection time point.
- Clinical activity ( PDAI)
- Routine laboratory parameters (hemoglobin, leukocytes, neutrophils, eosinophiles, basophiles, monocytes, lymphocytes, erythrocyte sedimentation rate, CRP, ferritin, iron and transferrin)
- Stool sampling - assessment of fecal calprotectin levels:

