### 9.3 DEFINITIONS OF INTEREST

#### **Clinical activity**

- Clinical remission among patients with CD: PCDAI<10 points during therapy with azathioprine.
- Clinically active disease among patients with CD: PCDAI points during therapy with azathioprine:
  - Mildly active disease: PCDAI >11<30
  - Moderately/severely active disease: >31

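### Time to loss of clinical remission counts only a raised PCDAI on azathioprine, so a flare treated with added Crohn's therapy, and possibly one that ends azathioprine, can be scored as no loss

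*Protocol*

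**What the plan says.** Section 9.2 lists, for patients with moderate/severe disease at inclusion who achieved clinical remission, "Median time to loss of clinical remission (PCDAI>11) with azathioprine". For the mild subset it lists "Median time to loss of clinical remission (PCDAI >10 ) with azathioprine". Section 9.3 defines remission as "Clinical remission among patients with CD: PCDAI<10 points during therapy with azathioprine" and defines clinically active disease with the same tie to azathioprine therapy. No event other than a PCDAI value is named.

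Section 6.3 treats the two likely responses to a flare differently. Stopping azathioprine is a listed reason why observation may end before week 96. Adding a drug is not: "The introduction of new treatments to CD during the follow up period will not lead to study discontinuation", provided azathioprine continues.

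Section 7.1 sets follow-up collection at "every 12 weeks up to week 96"; the chronogram adds week 8. The last chronogram column covers week 96 or discontinuation, and PCDAI is marked there. Section 6.3 and the footnote to that column list what to record at early discontinuation (date, last azathioprine intake and dose, reason) and do not mention PCDAI. Changes in Crohn's therapies and the reason for discontinuation are collected (section 7.1 and chronogram).

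**The concern.** One secondary objective in section 3.2 is the impact of azathioprine on maintaining clinical remission. When remission fails, a physician may add a therapy or change azathioprine. Under the stated event rule neither action counts as a loss, and either can keep the raised PCDAI out of the data.

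If another drug restores remission before the next visit, the endpoint credits azathioprine with that drug's effect. If azathioprine is stopped because of a flare, the only PCDAI showing the flare may be one that an analyst rules to be off azathioprine. Both paths push the estimate the same way, towards longer remission. There is no comparator arm in which the same error would show.

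**Working it through.** The protocol gives no design figure for this endpoint. Its only precision statement, in section 10.2, concerns a correlation and has no bearing here. The check is therefore a reading of the event rule, followed by an illustration.

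**Step 1. Trace each course of a flare through the rules.**

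| Course after a flare between visits | Follow-up | Is a loss recorded? |
|---|---|---|
| No treatment change, PCDAI still raised at next visit | continues | Yes |
| Crohn's therapy added, PCDAI still raised at next or a later visit on azathioprine | continues (6.3) | Yes, possibly late |
| Crohn's therapy added, PCDAI below cut-off at next visit and no later loss | continues (6.3) | No |
| Azathioprine stopped, PCDAI at discontinuation above cut-off | may end (6.3) | Unclear: depends on whether this PCDAI counts as on azathioprine |
| Azathioprine stopped, PCDAI at discontinuation missing or below cut-off | may end (6.3) | No |

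**Step 2. Inputs for the illustration.** True loss by week 96 is L. Section 2.1 reports "relapse rates of 40 to 60% were found with azathioprine" but gives no period; applying it to 96 weeks is an assumption. The hazard is taken as constant, with visits every 12 weeks (eight intervals). The share of flares masked by added therapy (m) and the share lost through an uncounted stop (f) are both assumptions; the protocol supplies neither.

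**Step 3. All flares counted, L = 0.60.** Remission at week t is 0.40^(t/96). The exact median is 96 × ln 0.5 / ln 0.4 = 72.6 weeks. On the visit grid, remission is 0.40^0.75 = 0.503 at week 72 and 0.40^0.875 = 0.449 at week 84, so the median reads week 84. Remission at week 96 is 0.40.

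**Step 4. Flares masked by added therapy.** Masked patients stay in the risk set, so apparent remission at week 96 is 1 − (1 − m)L.

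- L = 0.60, m = 0.10: 1 − 0.90 × 0.60 = 0.46. At week 84 it is 1 − 0.90 × 0.551 = 0.504, so the median reads week 96.
- L = 0.60, m = 0.25: 1 − 0.75 × 0.60 = 0.55. The median is not reached.
- L = 0.40, m = 0.25: 1 − 0.75 × 0.40 = 0.70, against 0.60. The median is not reached either way.

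For L = 0.60 the median is lost once m exceeds 1 − 0.50/0.60 = 0.167.

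**Step 5. Flares lost through an uncounted stop.** Suppose these patients are treated as censored between visits. With q = 1 − (1 − L)^(1/8) the loss per interval, each visit multiplies the Kaplan-Meier estimate by (1 − q)/(1 − fq).

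- L = 0.60 (q = 0.108): f = 0.25 gives about 0.50 at week 96, just low enough for the median to read week 96. f = 0.50 gives 0.62, and the median is not reached.
- L = 0.40 (q = 0.062): f = 0.25 gives 0.68 and f = 0.50 gives 0.77, against 0.60.
- If the PCDAI at discontinuation is counted and is above the cut-off in every such patient, f = 0 and the bias disappears.

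**The case against.** A reader might infer that any flare leading to an azathioprine stop is never counted and that the patient is censored as relapse-free. The documents do not support this. The chronogram schedules a PCDAI at discontinuation, so such a patient is due an assessment at that point. The protocol also states no censoring rule; that may sit in a SAP, which is not shown. The stopping path produces bias only if that PCDAI is missing, below the cut-off, or ruled off therapy.

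The masking path is also limited. A patient given added therapy keeps 12-weekly PCDAI follow-up, so the loss is missed only if the flare comes and goes between visits and no later visit shows one. Nothing in the protocol says how often that happens, so every share used above is assumed.

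It can further be said that the wording poses a deliberate on-treatment question, that this is a secondary endpoint in two subsets, and that section 9.2 separately reports clinical remission and the proportion still on azathioprine at each visit. Those points limit the importance. They do not remove the defect: persistence on azathioprine does not reveal a flare treated with a second drug, and the event rule leaves the discontinuation PCDAI open to either reading.

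Finally, not every stop is a relapse. Section 2.1 reports stops for intolerance, and counting all stops as losses would bias the median the other way.

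**Conclusion.** The point holds as a cheap improvement to a secondary endpoint. As written, a flare treated with added therapy that resolves before the next visit is scored as continued remission on azathioprine. Whether a flare that ends azathioprine counts is undefined. Both effects lengthen the apparent time to loss.

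The direction follows from the text; the size does not. Under an assumed 60% loss by week 96 and a constant hazard, masking 25% of flares raises apparent remission at week 96 from 0.40 to 0.55 and moves the median from week 84 to not reached. At an assumed 40% loss the median is not reached in any case, and the same masking raises remission from 0.60 to 0.70. With no flares masked and the discontinuation PCDAI counted and raised in every flare-driven stop, there is no bias. It would be wrong to state that the median is overstated by any particular amount.

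**What to change.** In sections 9.2 and 9.3, and in the synopsis, define loss of clinical remission as the earliest of:

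1. a PCDAI above a single agreed cut-point, stating that the PCDAI at the discontinuation visit counts;
2. the start of a new Crohn's therapy for active disease;
3. azathioprine stopped for relapse or lack of effect.

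Treat stops for intolerance as a competing event and report cumulative incidence alongside the median. Keep the PCDAI-only analysis as a sensitivity analysis. Name PCDAI in section 6.3 and in the chronogram footnote among the items to record at early discontinuation. The loss cut-offs in section 9.2 differ between the two subsets, and the remission cut-off differs between the synopsis and sections 9.2 and 9.3; these must be reconciled first.

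The cost is endpoint wording plus a start date and indication for each new Crohn's therapy, so that treatment planned from diagnosis is not counted. Therapy changes and the reason for discontinuation are already collected. The downside is a less favourable time to loss and some reliance on the physician's stated reason. The change concerns how outcomes are counted, not how patients are treated.

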### 9.3 DEFINITIONS OF INTEREST

#### **Clinical activity**

- Clinical remission among patients with CD: PCDAI<10 points during therapy with azathioprine.
- Clinically active disease among patients with CD: PCDAI points during therapy with azathioprine:
  - Mildly active disease: PCDAI >11<30
  - Moderately/severely active disease: >31

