Secondary Objective(s):	
 
•To explore the association of the fecal calprotectin assessment regarding clinical and endoscopic outcomes.
 
•To explore the association of fecal calprotectin levels with clinical outcome throughout a follow up period of 96 weeks.
 
•To explore the association of fecal calprotectin levels with endoscopic activity throughout a follow up period of 96 weeks.
 
•To evaluate the impact of azathioprine in inducing clinical remission at week 12.
 
•Among patients who achieve clinical remission with azathioprine, to evaluate the maintenance of clinical remission up to week 96.
 
•To evaluate the impact of azathioprine in inducing endoscopic remission at week 96.
 
•To evaluate the impact of azathioprine in maintaining endoscopic remission throughout a follow up period of 96 weeks.
 
•To evaluate the rate of azathioprine persistence throughout a follow up period of 96 weeks
 

	
 
•To evaluate the time until loss clinical remission
 

Study Design:	
Multicenter, prospective, observational study designed to gather and analyze data on a consecutive cohort of subjects with CD who initiated therapy with azathioprine, according to physician's clinical decision. There is no imposed experimental intervention and prescribing decisions from the study physicians will be independent of patient's participation in this study.
 
The maximum overall duration of observation for each patient is 96 weeks since the start of observation period (Day 1).

Inclusion Criteria:	
Study patients must fulfill the following criteria:
 
 
1. Male or female patients, <18 years;
 
2. Patients who are registered in the GEDII Registry;
 
3. Patients who have been treated with exclusive polymeric diet and start azathioprine at diagnosis
 
 
AND who meet one of the following:
 
 
o Moderate/Severe disease (PCDAI>31) at start of study with fecal calprotectin levels > 100 ug/g
 
o Mild disease (PCDAI>11<30) with fecal calprotectin levels > 100 ug/g and/or Endoscopic activity (Simple endoscopic score for Crohn's disease [SES-CD] ≥ 3)
 
 
 
4. Patients who gave their informed consent.
 

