	
point.
 
 
•Fecal calprotectin levels and endoscopic activity (Simple endoscopic score for Crohn's disease [SES-CD]) at week 96.
 
•Proportion of patients with clinical remission (PCDAI <math>\leq</math> 10) at each data collection time up to week 96.
 
•Proportion of patients who achieve endoscopic remission (SES-CD <math>\leq</math> 2) at week 96.
 
 
Among patients with moderate/severe CD (at inclusion) and who maintain clinical remission with azathioprine:
 
 
•Median time to loss of clinical remission (PCDAI>11) with azathioprine
 
 
Among patients with mild Crohn's disease at study inclusion and who maintain clinical remission with azathioprine:
 
 
•Median time to loss of clinical remission (PCDAI>11) with azathioprine
 
•Physician reported clinical outcome (PCDAI) at each data collection time points.
 

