## 6 STUDY POPULATION

### 6.1 INCLUSION CRITERIA

Study patients must fulfill the following criteria:

1. Male or female patients, <18 years old
2. Patients who are registered in the GEDII Registry;
3. Patients who induce remission with polymeric diet and start azathioprine at diagnosis

**AND** who meet one of the following:

- o Moderate/Severe disease (PCDAI>30) at start of study
- o Mild disease (PCDAI<30) with fecal calprotectin levels > 100 ug/g and/or Endoscopic activity (Simple endoscopic score for Crohn's disease [SES-CD] ≥ 3

4. Patients who gave their informed consent.

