### 9.2 SECONDARY ENDPOINTS

- **Fecal calprotectin** levels assessed at each data collection time point.
- **Fecal calprotectin** levels and **clinical activity (PCDAI)** at each data collection time point.
- **Fecal calprotectin** levels and **endoscopic activity (Simple endoscopic score for Crohn's disease [SES-CD])** at week 96.
- Proportion of patients with **clinical remission** (PCDAI<10) at each data collection time up to week 96.
- Proportion of patients who achieve **endoscopic remission** (SES-CD ≤ 2) at week 96.
- Proportion of patients on treatment with **azathioprine** at each data collection time point up to week 96.

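### PCDAI rules for entry, severity group, remission and loss of remission disagree between sections of the protocol and leave some scores unclassified

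*Protocol*

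**What the plan says.** **Remission.** Section 9.3 gives "Clinical remission among patients with CD: PCDAI<10 points during therapy with azathioprine", and the endpoint in section 9.2 uses the same cut ("PCDAI<10) at each data collection time up to week 96"). The synopsis (section 1) lists "Proportion of patients with clinical remission (PCDAI \leq 10) at each data collection time up to week 96", that is, 10 or less.

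**Loss of remission.** Section 9.2 gives "Median time to loss of clinical remission (PCDAI>11) with azathioprine" for patients with moderate/severe disease at inclusion and "Median time to loss of clinical remission (PCDAI >10 ) with azathioprine" for those with mild disease. The synopsis uses above 11 for both groups.

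**Moderate/severe disease.** The entry rule in section 6.1 is "Moderate/Severe disease (PCDAI>30) at start of study", with no calprotectin condition. The synopsis has "Moderate/Severe disease (PCDAI>31) at start of study with fecal calprotectin levels > 100 ug/g". Section 9.3 also puts this band above 31.

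**Mild disease.** Section 9.3 has "Mildly active disease: PCDAI >11<30", that is, strictly between 11 and 30. The synopsis and section 9.2 use the same range. Section 6.1 requires only a score below 30. In both sets of entry criteria, mild patients also need calprotectin above 100 ug/g and/or SES-CD of 3 or more.

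**Use in the analysis.** Section 10.1 fits the GEE models separately for the mild and moderate/severe groups on Day 1. It also reports remission proportions for patients with active and with non-active disease at inclusion. No section says which wording takes precedence.

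**The concern.** The same patient can be eligible or not, and in remission or not, depending on the page consulted. Around 11 centres are to apply the entry criteria, so two sites acting in good faith could enrol different populations.

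Four results depend on these cuts:

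- the number and type of patients enrolled;
- the clinical remission proportion at each visit;
- the date on which remission is counted as lost;
- the Day 1 severity group used for the GEE.

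A missing lower bound for mild disease has a further effect. One secondary objective is to evaluate induction of clinical remission at week 12. A patient admitted under 6.1 with a score below 10 meets the remission definition before follow-up starts. If still below 10 at week 12, that patient counts towards the proportion, although nothing was induced.

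**Working it through.** The protocol's only calculated figure, the correlation power in section 10.2, uses no PCDAI cut. It reproduces: Φ[(atanh 0.75 − atanh 0.50)·√(80 − 3) − 1.645] = 0.981, in line with the stated figure of more than 95%. It has no bearing on this point.

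**Step 1. Apply each rule to the boundary scores.** The last two columns show the severity group whose PCDAI condition the score meets. The calprotectin and endoscopy conditions come on top.

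| Score | Remission, synopsis (≤10) | Remission, 9.2 and 9.3 (<10) | Loss >11 (synopsis both groups; 9.2 moderate/severe) | Loss >10 (9.2 mild) | Band in 9.3 | Entry, synopsis | Entry, 6.1 |
|---|---|---|---|---|---|---|---|
| 9 | yes | yes | no | no | remission | none | mild |
| 10 | yes | no | no | no | none | none | mild |
| 11 | no | no | no | yes | none | none | mild |
| 12 | no | no | yes | yes | mild | mild | mild |
| 29 | no | no | yes | yes | mild | mild | mild |
| 30 | no | no | yes | yes | none | none | none |
| 31 | no | no | yes | yes | none | none | moderate/severe |
| 32 | no | no | yes | yes | moderate/severe | moderate/severe | moderate/severe |

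**Step 2. Separate what depends on the step size.** The protocol does not state the increments in which PCDAI moves, so both cases are assumptions.

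- *Whole-number scores possible.* Every row above can occur.
- *Steps of 2.5 or 5 only.* The first score above 10 is 12.5 or 15, and the first above 30 is 32.5 or 35. Then >10 and >11 select the same patients, as do >30 and >31, and those two conflicts disappear.

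Four problems remain in either case:

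1. A score of 10 is remission in the synopsis but not in 9.2 or 9.3. Within 9.2 it is neither remission nor loss, in either severity group.
2. A score of 30 meets no entry rule in 6.1 or the synopsis and has no band in 9.3.
3. Scores from 0 to 11 meet the PCDAI part of mild entry in 6.1 but not in the synopsis. Those below 10 already satisfy every version of remission.
4. A patient scoring above 31 with calprotectin of 100 ug/g or less is eligible under 6.1 and not under the synopsis. That patient is already below the 200 ug/g threshold of the primary endpoints on Day 1.

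**Step 3. Size.** The two remission rules differ only at exactly 10. If k of the 80 patients score 10 at a visit, the proportion differs by 100 × k/80 points, taking all 80 as the denominator. One patient gives 100 × 1/80 = 1.25 points. As an illustration only, four patients would give 100 × 4/80 = 5 points. The documents do not give k. Within a severity group the step per patient is larger, but the group sizes are not stated.

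**The case against.** The strongest reply has four parts.

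*The primary endpoints contain no PCDAI cut.* All three are defined by calprotectin below 200 ug/g. This stands: the remission and loss conflicts affect secondary endpoints. The entry conflicts reach the primary endpoints only indirectly, through the denominator.

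*Some conflicts may be empty.* If scores move in coarse steps, the differences between 10 and 11 and between 30 and 31 as cuts have no effect. This stands for those two, but not for the four problems that survive.

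*The missing bound in 6.1 may be a slip.* The group is labelled mild, 9.3 defines mild with a lower bound, and 9.2 repeats that bound for the mild group's time-to-loss endpoint. This is a fair reading. However, sites enrol from 6.1 as written, and the planned non-active subset at inclusion fits only a population without the lower bound. The synopsis repeats that subset in its statistical methods, against its own entry rule.

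*The analysis plan could settle it.* It could settle the endpoint cuts, but not eligibility, which is applied at enrolment from the protocol.

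Two stronger readings are tempting. A reader might infer that the remission proportion shifts by the share of visits scoring 10 to 11. It does not, because 11 is non-remission under every version. A reader might also infer that the >10 rule makes the mild group's median time to loss shorter by definition. It makes that time no longer than under >11, and shorter only if some patients score above 10 and up to 11. The protocol plans no comparison of the two medians.

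**Conclusion.** The contradictions are in the current text and should be resolved before the data are analysed. Four hold whatever the PCDAI step size: a score of exactly 10 for remission, the score of 30 with no place, the lower bound of mild entry, and the calprotectin condition for moderate/severe entry. Two more, on loss of remission and on the moderate/severe cut, apply only if scores can fall above 10 and up to 11, or above 30 and up to 31.

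The effect on the clinical remission proportion is 1.25 points per patient scoring exactly 10, assuming a denominator of 80. The total cannot be estimated from the documents. Nor do they show how many patients would be enrolled under one entry wording and refused under the other. A reader might infer that the primary endpoint definition is itself compromised; the documents do not support that. They also do not show which cut-points are right, and none is endorsed here.

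**What to change.** - Reconcile the synopsis and sections 6.1, 9.2 and 9.3 to one set of exhaustive, mutually exclusive PCDAI bands, chosen by the sponsor and worded identically in all four places.
- Define loss of remission as the complement of remission, with the same rule in both severity groups.
- State one calprotectin entry rule for moderate/severe disease.
- State whether patients already in clinical remission on Day 1 are eligible. If they are, report them separately from patients in whom remission is induced. Align the active and non-active subsets in section 10.1 and the synopsis with that decision.
- State the PCDAI step size, so that the boundaries can be checked.

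No extra data are needed. The cost is a wording amendment with the ethics committee submission that section 12.1 requires, and a documented decision on how to classify anyone enrolled under the other wording.
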